### ***Measures***

Baseline and follow-up self-administered measures are reliable and valid among adults. Data will be collected via the MyDataHelps app, online via Qualtrics, or by phone with study staff. Please refer to Table 1 for a full list of study measures and administration time points.

Daily mental health symptom assessments will be collected via the MyDataHelps app. During app set-up, participants will be prompted to allow the app to send them notifications; study staff will encourage participants to enable notifications. A notification will be automatically generated on their smartphone on a daily basis and will appear as follows: "On a scale of 1 to 10, what was your average mood today?" Participants will then respond in the MyDataHelps app. Participants will be asked to complete this daily, one-item assessment throughout the duration of their study involvement.

Participants may also be asked to complete a weekly suicide risk assessment question via the MyDataHelps app. Participants would receive a notification to complete the weekly assessment within the app. The question will appear as: "On a scale from 0 (Not at all confident) to 10 (Extremely confident), how confident are you that you will NOT attempt suicide in the future?" (Czyz, et al., 2016).

Participants will also be asked about their frequency of use of mental health, physical health, and mindfulness apps via the MyDataHelps app. This assessment will take place as part of the baseline and all follow-up surveys. The questions are adapted from mental health app survey questions developed by Kern, et al., 2018, and will appear as follows:

- How frequently did you use mental health apps within the past 6 months? (Never, Less than monthly, Monthly, Weekly, Daily or almost daily)
- How frequently did you use physical health apps within the past 6 months? (Never, Less than monthly, Monthly, Weekly, Daily or almost daily)
- How frequently did you use mindfulness or meditation apps within the past 6 months? (Never, Less than monthly, Monthly, Weekly, Daily or almost daily)

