### Surveys

Participants will be asked to complete four surveys, including a baseline survey at the time of enrollment and three follow-up surveys, which will be designed to complement in-clinic assessments completed as a part of standard outpatient mental health care. To the extent possible, redundancy with in-clinic assessments (i.e., due to the Measurement-Based Care program) will be avoided. The first follow-up survey will occur at the end of 6 weeks post-enrollment, the second at the end of 18 weeks post-enrollment and the third at the end of 12 months post-enrollment.

Depending on waitlist length for outpatient mental health services, there may be variation in whether participants have engaged with clinical care by the time they complete their follow-up survey(s). Surveys will be administered by the predetermined schedule regardless of whether participants have engaged with care. The rationale for this decision, rather than scheduling follow-up surveys to coincide with the initiation of outpatient care:

1. There is a possibility that participants may never engage with outpatient care, and these non-engagers would never receive follow-up surveys
2. Waitlist time often varies between recruitment sites (i.e., UHS tends to have a shorter waitlist for care), which would create measurement biases (e.g., UHS patients may consistently engage in care with less time to engage with the app-based intervention)
3. Participants may be receiving other mental health care (e.g., via primary care), making it less important to time follow-up surveys with the initiation of outpatient mental health services
4. The existing timeline ensures all participants randomized to the groups receiving app-based interventions have received a reasonable 'dose' of the intervention prior to assessment
5. The existing timeline ensures that measurement will take place at generally the same time frame for all participants

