### ***Self-Report Surveys***

Participants will complete four surveys, including a baseline survey and three follow-up surveys. All surveys will be self-administered via the MyDataHelps study app. In the case of technological difficulties, the study team does have paper copies of the baseline and follow-up surveys available, and the surveys may be administered in person or by phone. The baseline survey will take about 25 minutes. Survey questions include demographics, overall physical and mental health symptoms and diagnoses, substance use, environment, use of mobile technology and health apps, and social network and support. For each of the three follow-up assessments, participants will complete an approximate 20-minute survey with similar content as the baseline survey. If necessary, the survey can be administered by study staff via phone who will read survey questions to the participant and record their responses. When participants are due for their surveys, they will receive an email or app notification that their survey is available via the MyDataHelps app. If participants do not respond to the questionnaires, and have not indicated that they do not wish to participate in the study, a reminder will be sent by email, phone, mail, or text message.

The first follow-up survey will occur at the end of 6 weeks post-enrollment, the second at the end of 18 weeks post-enrollment, and the third at the end of 12 months post-enrollment. Each of these time-points may occur near the time of an in-person outpatient mental health clinic appointment, at which participants may be asked to answer some of the same questions that are contained in the study surveys. To reduce participant burden, study staff will monitor upcoming appointments and participants will receive a version of the survey without redundant items if they have an appointment within 1 week of their follow-up survey due date. They will still complete the remainder of the follow-up survey and be paid the same amount for their time. Additionally, participants who do not show for clinic appointments will still be able to complete the follow-up assessments via standard study procedure.

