### ***Data Collected from Phones and Sensors***

Data that may be collected from participant smartphones and periodically transmitted to a secure database may include:

- Phone orientation
- Phone acceleration
- Frequent locations
- Voice
- Social network indicators (call and text frequency, etc.)
- Screen time
- App usage

Words typed are stripped from their context and syntax, thus preventing the content of any messages from being deciphered. The study app does not collect phone numbers or email addresses, photos or videos, passwords, credit card numbers, or any other secure or personally identifying information.

Wearable device (Fitbit or Apple Watch) costs will be covered by the Precision Health award budget (devices will not be provided for free by Apple or Fitbit). Data collected from the Apple Watch or Fitbit include:

- Heart rate
- Physical activity (steps, minutes, type of activity, estimated calories)
- Geospatial location
- Sleep

Data collected from participant use of SilverCloud or Headspace will include general usage data, such as time spent utilizing the app per day.

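### The fixed 6-month look-back in the app-use questions mixes use before and after enrolment at 6 and 18 weeks and leaves about weeks 18 to 26 unasked

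*Combined protocol and SAP*

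**What the plan says.** The Measures section lists three frequency questions: "How frequently did you use mental health apps within the past 6 months", "How frequently did you use physical health apps within the past 6 months" and "How frequently did you use mindfulness or meditation apps within the past 6 months". Each has five options running from 'Never' to daily or almost daily use. On timing it says "This assessment will take place as part of the baseline and all follow-up surveys". Table 1 agrees, listing the measure at baseline, 6 weeks, 18 weeks and 12 months. No follow-up version with another look-back appears anywhere.

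The Surveys section counts the follow-ups from enrolment: "The first follow-up survey will occur at the end of 6 weeks post-enrollment, the second at the end of 18 weeks post-enrollment", with the third at 12 months.

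Two other sources bear on app use, both under Data Collected from Phones and Sensors. For the intervention apps, "Data collected from participant use of SilverCloud or Headspace will include general usage data", including daily time in the app. Phone-level app usage appears too, but only in a list of data that may be gathered.

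The Analysis Plan names app use among the areas to be assessed with both subjective and objective data. Under Phase 1, the EF+SF arm receives feedback only and is assigned neither intervention app.

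**The concern.** A follow-up question on app use should describe use since enrolment, or at least since the previous survey. A 6-month look-back asked 6 weeks after enrolment describes mostly the period before the trial. It also overlaps heavily with what the participant has already reported at baseline.

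The timing matters because Aim 1 concerns the period on the waitlist, and Screening and Recruitment puts the usual wait at 3 to 10 weeks. The 6-week survey is therefore the follow-up closest to that period, and it is also the one whose window reaches furthest back before enrolment.

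What is at stake is mainly the EF+SF arm. If its participants take up mental-health or mindfulness apps on their own, the contrast with the app arms becomes harder to interpret. These items are the only scheduled measure in Table 1 that would show it. An EF+SF participant who answers 'Weekly' at baseline and again at 6 weeks may have continued throughout or may have stopped at enrolment. Both histories give a truthful 'Weekly'.

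**Working it through.** The plan states no figure on this point, so there is nothing to reproduce. The check is interval arithmetic.

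**Inputs**
- Look-back W = 6 months (Measures), taken as 26 weeks. A value of 24 weeks is also tried, because the plan does not define a month in weeks.
- Survey times t = 6 weeks, 18 weeks and 12 months after enrolment (Surveys; Self-Report Surveys), with 12 months taken as 52 weeks.
- The baseline survey is taken to coincide with enrolment (Surveys).

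**Formulas**
- Window covered: from week t − W to week t, with enrolment at week 0.
- Share before enrolment: max(0, W − t) / W.

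| Survey | Window in weeks (W = 26) | Weeks before enrolment | Share before enrolment | Share if W = 24 |
|---|---|---|---|---|
| 6 weeks | −20 to 6 | 26 − 6 = 20 | 20/26 = 77% | 18/24 = 75% |
| 18 weeks | −8 to 18 | 26 − 18 = 8 | 8/26 = 31% | 6/24 = 25% |
| 12 months | 26 to 52 | 0 | 0% | 0% |

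The weeks before enrolment are also the weeks shared with the baseline window: 20 at the 6-week survey and 8 at the 18-week survey.

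**Gap.** The 18-week window ends at week 18 and the 12-month window starts at week 52 − 26 = 26. That leaves 26 − 18 = 8 weeks in no follow-up window (52 − 24 − 18 = 10 weeks if W = 24).

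**What the answers can still show.** Taken at face value, 'Never' at baseline followed by any other answer at 6 weeks means new use since enrolment. 'Never' at 6 weeks followed by any other answer at 18 weeks places the use in weeks 6 to 18. The 12-month answer refers only to time in the trial. What cannot be separated is use among people who already used such apps before enrolment.

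**What the logs cover.** The Headspace and SilverCloud records describe use of the assigned app in App+SF and App+EF+SF. They give nothing for EF+SF, and they do not show use of other apps in any arm.

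**The case against.** The best defence has four parts.

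1. **Feasibility does not depend on these items.** Use of the assigned app is recorded directly, and the App-Based Interventions section has staff act on records of non-use. This stands. It confines the problem to app use outside the study, above all in EF+SF.

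2. **The items are not uninformative.** A reader might infer that the answers cannot show app use during the trial at all. The documents do not support that. The 12-month window is wholly in the trial, about 69% of the 18-week window is (18/26), and a change from 'Never' is informative even at 6 weeks.

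3. **The plan does not call these items a contamination measure.** This is correct. They ask about classes of app in general and do not separate assigned from off-study apps. Changing the look-back alone would still leave the two merged in the app arms, so the fix has to alter content as well.

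4. **A constant time frame is a defensible choice.** The items are adapted from a published survey, and one window at every wave keeps answers formally comparable with baseline. Randomisation should also balance pre-trial use across arms on average, so the window does not by itself create a false difference between arms. Both arguments have weight and keep the severity low. Neither makes the 6-week answer a measure of use since enrolment.

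Phone-level app usage might fill the gap, but the plan says only that it may be collected.

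**Conclusion.** The point holds in a limited form. With one 6-month look-back at every survey, about 77% of the 6-week window and 31% of the 18-week window precede enrolment (75% and 25% if 6 months is read as 24 weeks). About 8 weeks, from week 18 to week 26, are asked about in no follow-up survey. The self-report items therefore cannot isolate use since enrolment at 6 and 18 weeks, and they cannot date app use in EF+SF among people who used such apps before.

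A reader might go further and say that new users will report one category too low. Weekly use for 6 weeks is 6 occasions in 26 weeks, or 0.23 per week, and daily use is 42 occasions, or 1.6 per week. That reading requires respondents to average over the whole window, and nothing in the documents says that they do. Someone now using an app daily may simply answer 'Daily'.

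The severity is minor. App use is one of several areas the Analysis Plan lists, no sample size or named effectiveness endpoint rests on these items, and the symptom outcomes are untouched. The conclusion assumes that the items are asked as printed and that the baseline survey falls at enrolment.

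**What to change.** Keep the 6-month look-back at baseline. At 6 weeks, 18 weeks and 12 months, ask all three items about use 'since your last study survey', with the same five frequency options. In the mental-health and mindfulness items, add 'other than any app assigned to you by this study', and report off-study use by arm. For participants who complete every survey, the follow-up windows then join end to end, which closes the gap at weeks 18 to 26.

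A fixed four-week look-back at each follow-up would be worse for coverage. It would miss weeks 0 to 2, 6 to 14 and 18 to 48, which is 2 + 8 + 30 = 40 of 52 weeks.

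The cost is rewording three items in three in-app surveys and a short IRB amendment. There is a small downside. Follow-up answers no longer share the baseline time frame, and the follow-up windows differ in length: about 6, 12 (18 − 6) and 34 (52 − 18) weeks. Answers should therefore be compared between arms at the same survey, not read as a trend over time.

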### ***Electronic Health Record Data***

Participation in the study will allow for the use of the patients' electronic health record (EHR) data, outcomes registries (including local, state, national, and international, such as the National Death Index), prescription-related data accessed via the SureScripts Health Information Network, administrative data, and other sources of health and outcomes data stored in the University of Michigan Research Data Warehouse. Patients agree to be re-contacted in the event that researchers would like to consent the patients for additional studies requiring further testing, data, or feedback. They may decline any further study opportunities without any impact on their participation or compensation for this study.

### ***Biological Specimen***

A biological specimen will be obtained as part of this study, which will be facilitated by the University of Michigan Medical School Central Biorepository (CBR). The CBR will facilitate ordering of DNA collection kits, as well as the processing and storage of DNA samples. The Michigan Genomics Initiative (MGI) (HUM00071298) is a collaborator in this study, and MGI will cover the costs of DNA collection kits, processing, and storage that are charged by the CBR. Participants that have previously participated in MGI will not receive genetic analyses as part of this protocol, given that their biological specimen has already been submitted to the CBR.

Participants will be sent DNA collection kits via postal mail and asked to provide a small sample of saliva. Participants will return samples to study team members in a provided self-addressed, stamped return envelope. Participants also have the option to provide a saliva sample in person, if needed or preferred.

Genetic analyses will be carried out on the DNA sample. Incidental findings from the DNA analysis will not be shared with the participant or the participant's physician.

If participants do not submit a DNA sample and have not indicated that they do not wish to participate in the study, they will be contacted by a study team member by phone, email, text message, or mail as a reminder. Study staff will be trained to discuss confidentiality and privacy of genetic data to improve participant adherence with the request to submit a DNA sample.

### ***Data Collected from Phones and Sensors***

Data that may be collected from participant smartphones and periodically transmitted to a secure database may include:

- Phone orientation
- Phone acceleration
- Frequent locations
- Voice
- Social network indicators (call and text frequency, etc.)
- Screen time
- App usage

Words typed are stripped from their context and syntax, thus preventing the content of any messages from being deciphered. The study app does not collect phone numbers or email addresses, photos or videos, passwords, credit card numbers, or any other secure or personally identifying information.

Wearable device (Fitbit or Apple Watch) costs will be covered by the Precision Health award budget (devices will not be provided for free by Apple or Fitbit). Data collected from the Apple Watch or Fitbit include:

- Heart rate
- Physical activity (steps, minutes, type of activity, estimated calories)
- Geospatial location
- Sleep

Data collected from participant use of SilverCloud or Headspace will include general usage data, such as time spent utilizing the app per day.

## **MHEALTH INTERVENTIONS**

### *Standard Feedback (SF)*

All participants will receive the feedback that is standard with the Apple Watch or Fitbit devices. Both sensors provide feedback on activity level, heart rate, and progress toward daily activity goals on the device itself. For the Apple Watch, this also includes feedback from the iPhone's "Activity" and "Watch" apps. For Fitbit users, this includes feedback in the "Fitbit" app.

### *Enhanced Feedback (EF)*

Participants randomized to receive enhanced feedback will receive this feedback from the MyDataHelps study app. This includes varying types of text and visual feedback based on data collected through the app. Feedback will be displayed to participants on a dashboard in the app or delivered via pop-up notifications. Participants will receive a combination of text and visual feedback.

Examples of potential text feedback:

- A summary statement connecting behaviors (e.g. "On Tuesday, your mood was a 9. That night, you slept 6 hours. Your mood was a 7 the next day.")
- Empathetic feedback about behavioral patterns (e.g. "You had a tough week. On Tuesday, when you were at the hospital for 12 hours, your mood was a 6. What have you done in the past to help your mood when you had a hard day?")
- A motivational tip (e.g. "It seems like you have had a tough week. Hang in there – you've survived worse!")

Examples of potential visual feedback:

- A graph plotting one data type over time (e.g. hours of sleep for the past week)
- A graph plotting the relationship between different data types over time (e.g. mood and sleep hours for the past month)

We also plan for some feedback to be customized based on subjects' mood, activity, and sleep data. For example, subjects who slept for less than 6 hours on average in the past week might receive different feedback than those who slept more.

### *App-Based Interventions*

Participants randomized to the groups receiving the apps will be asked to install an mHealth app onto their smartphone. The two apps that will be used are Headspace, an app designed to train the user in mindfulness practices, and Silvercloud, an app designed to deliver cognitive behavioral therapy. These apps were selected because of evidence of efficacy and applicability across a wide range of mental health symptoms. Participants receiving apps will be computer-assigned to receive one of the two options. Participants who were recruited with <2 weeks prior to their scheduled appointment (and thus not included in the initial randomization) will receive access to one of the two apps at the time of their intake appointment, also based on computer random assignment.

App notifications will encourage participants to use the apps regularly. If user data indicates that a participant is not using the apps, study staff will contact the participant via app notification, phone call, email, letter, or text message. SilverCloud allows for integration of a health coach as a supportive role for increasing engagement, largely through asynchronous messaging. Study staff will be trained in the role of the health coach and will engage with participants through the app to promote app use, personalization, and overall engagement. For both apps, study staff will provide ongoing technical assistance and address any participant barriers to app use.

### **ANALYSIS PLAN**

A primary goal is to obtain information about the feasibility and acceptability of the use of app-based interventions and enhanced feedback in response to mobile health device use, as well as to estimate the distribution and variability of potential primary and secondary outcomes of interest. Data will be examined using standard univariate summary measures, bivariate statistical tests of association, and graphical displays. We will assess subjective and objective data in areas including mental health and physical health measures, substance use, and app use. This will assess responsiveness to the interventions as well as how best to provide clinicians with useful patient data that may help inform treatment decisions. This is a primary outcome for future work. Additional outcomes to be assessed are listed in Table 1.

We will calculate means and standard deviations for participant characteristics and outcomes measures at each assessment and also for change scores. With outcomes that are categorical, we will use the Chi square test, and with outcomes that are continuous, we will use t-tests to make comparisons.

We will also conduct baseline and ongoing analyses of the presence of genotype x stress interaction among this sample. For example, as a baseline analysis, we will investigate association between each variant/haplotype and PHQ (baseline) scores using linear regression. To explore gene x environment interactions, we will assess for association between each variant/haplotype and PHQ (change) scores.

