## **RESEARCH DESIGN AND METHODS**

This study will have **two phases**, each with different study designs:

**Phase 1** will cover the period while individuals are waiting for care. The design of this phase is a randomized clinical trial, wherein participants are randomly assigned to one of three study conditions that vary by the type of Mobile Health (mHealth) intervention they can receive.

**Phase 2** begins when a participant has a first appointment for outpatient mental health care, and uses a cohort study design for measuring outcomes associated with clinic-based treatments.

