## **Screening and Recruitment**

Participant screening and recruitment will be managed by study staff. All study team members are required to complete team/study training and all appropriate regulatory training and disclosures.

The study will recruit 4,500 participants via patients at Michigan Medicine and student patients at University Health Service (UHS). Potential study participants will include adult patients (age 18+) that are scheduled for an intake mental health appointment, pre-screening mental health appointment, on the waitlist/referral list, or identified as a potential patient seeking mental health at either Michigan Medicine or UHS. These appointments are generally scheduled with a 3-10 week waiting period. Patients will be invited to participate in the study as soon as possible after scheduling their appointment in order to best maximize participation during their full waiting period.

A waiver of HIPAA authorization is requested in order for study staff to:

- 1) Receive daily lists of patients for whom a mental health intake appointment has been scheduled at each recruitment site
- 2) Access the Michigan Medicine and UHS electronic health records to confirm eligibility of listed patients and obtain contact information

Study staff will employ the following **recruitment strategies** to contact, screen, and enroll potential participants:

1. At the time of scheduling their intake mental health appointment, patients may be informed by call center staff that they may be contacted about a new study.

2. Daily lists of newly scheduled appointments and individuals on the waitlist/referral list will be generated by the Michigan Medicine Department of Psychiatry call center, UHS scheduling, or from the Research Data Warehouse (RDW) and provided to study staff.
3. Using existing Research Data Warehouse information, a patient is prospectively identified as someone who meets the study criteria during the screening process. Potentially eligible patients may be contacted by email/text message/phone call to introduce the study, with an invitation to contact the study team by phone or email if interested in participating.
4. Prior to contacting patients by phone/text message/phone call, study staff will complete preliminary screenings via listed patients' electronic health records to determine whether basic, objective inclusion criteria are met (e.g., scheduled outpatient mental health appointment, age 18+).

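### The analysis plan names no method for ordered outcomes; read as an ordinary unordered test, its chi-square rule ignores the order of the five-level app-use items and loses power against modest shifts

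*Combined protocol and SAP*

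**What the plan says.** The Analysis Plan sorts outcomes into two classes. For one, "With outcomes that are categorical, we will use the Chi square test"; for the other, "with outcomes that are continuous, we will use t-tests to make comparisons". It mentions no third, ordinal class, and names no trend test, rank test or ordinal model.

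The Measures section defines three items on how often the participant used mental health, physical health and mindfulness apps over the past 6 months. Each is answered on the scale "Never, Less than monthly, Monthly, Weekly, Daily or almost daily". Table 1 schedules them at baseline, 6 weeks, 18 weeks and 12 months.

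They count as outcomes on two grounds. The Analysis Plan states "We will assess subjective and objective data in areas including mental health and physical health measures, substance use, and app use", and it adds "Additional outcomes to be assessed are listed in Table 1". It does not say which of the two classes the items belong to.

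**The concern.** Five labelled answers fall most naturally under the categorical rule, and an unqualified chi-square test on an arm-by-category table is ordinarily the Pearson test. That test has (2−1)(5−1) = 4 degrees of freedom for two arms and (3−1)(5−1) = 8 for three. Its p-value does not change if the five categories are put in any other order, so the information that Weekly lies between Monthly and Daily is not used.

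At stake is the power to show that one arm moves people towards more, or less, frequent use. The contrast most exposed is App+EF+SF against App+SF: both arms receive an app and they differ only in enhanced feedback, so a small shift is plausible there.

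**Working it through.** The plan gives no power or sample-size figure to reproduce. What follows measures the loss under stated assumptions.

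**Inputs from the documents.** Total N is 4,500 (Screening and Recruitment); "participants are randomly assigned to one of three study conditions" (Research Design and Methods); five ordered levels (Measures).

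**Assumptions.** Two-sided alpha 0.05. Equal allocation, so 4,500/3 = 1,500 per arm at most, with 750 as a missing-data scenario. The arms differ by a common odds ratio (OR) across all cut-points. Shares over the five levels, from Never upwards: flat (20% each), middle (30/20/15/20/15%), skewed to Never (50/20/10/10/10%), and a fourth set of 40/20/12/15/13%.

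**Formulas, two arms of n each with shares p and q.**

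- Pearson, 4 df: λ = n Σ (p_k − q_k)² / (p_k + q_k).
- Rank test, 1 df: with m = (p + q)/2 and midrank scores s_k = Σ_{j<k} m_j + m_k/2, let d = Σ (q_k − p_k) s_k and v = Σ m_k s_k² − (Σ m_k s_k)². Then λ = n d² / (2v).
- Power is the chance that a noncentral chi-square with that λ exceeds the 5% critical value: 9.49 on 4 df, 3.84 on 1 df.

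**Worked case: middle distribution, OR 1.20, n = 1,500.** The shifted shares are 26.3/19.1/15.3/21.8/17.5%.

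- Pearson: λ = 1,500 × (0.002410 + 0.000190 + 0.000028 + 0.000756 + 0.001887) = 1,500 × 0.005271 = 7.91; power 59.9%.
- Rank test: d = 0.02894, v = 0.07944; λ = 1,500 × 0.0008375 / 0.15888 = 7.91; power 80.3%.

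The two noncentralities agree. Under a consistent shift, nearly all the signal lies in the ordered component, so Pearson spends three further degrees of freedom with almost nothing to find there. With the 40/20/12/15/13% shares, λ = 7.71 for both tests, and power is 58.6% against 79.3%.

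**Range over the four distributions.**

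| n per arm | OR | Pearson | Rank test |
|---|---|---|---|
| 1,500 | 1.1 | 17–18% | 29–32% |
| 1,500 | 1.2 | 56–60% | 77–81% |
| 1,500 | 1.3 | 90–92% | 97–98% |
| 1,500 | 1.5 | about 100% | about 100% |
| 750 | 1.2 | 29–32% | 48–51% |
| 750 | 1.3 | 58–62% | 79–82% |
| 750 | 1.5 | 95–96% | 99% |

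**Equivalent sample size.** For 80% power, λ must be 7.85 on 1 df and 11.94 on 4 df, a ratio of 11.94/7.85 = 1.52. For a three-arm comparison it must be 9.63 on 2 df and 15.02 on 8 df, a ratio of 1.56. These ratios hold only for a consistent shift.

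**Simulation check** (4,000 runs, middle distribution, OR 1.20, 1,500 per arm): Pearson 59.5%, Wilcoxon 79.8%, t-test on scores 1 to 5 79.8%. With no difference between arms, all three reject in about 5% of runs.

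**Counter-example.** Compare 30/20/15/20/15% with 33/17/11/22/17%, where both ends gain at the expense of the middle. Pearson: λ = 1,500 × 0.012217 = 18.3, power 95%. Rank test: λ = 0.09, power 6%.

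**The case against.** A reader might infer that the plan prescribes a Pearson test for these items. It does not: it never uses that name and never assigns the items to a class. It also states "We will calculate means and standard deviations for participant characteristics and outcomes measures at each assessment and also for change scores", which leaves room to score the answers 1 to 5 and use a t-test; on that reading the simulation shows no loss. This stands, and it makes the point conditional. It does not remove it, because labelled categories with no ordinal rule still point most naturally to chi-square, and a plan should not leave the choice open.

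A reader might also infer a general loss equal to about half as many participants again. That holds only for a consistent shift. Pearson is a valid omnibus test, and it does far better against some non-monotone differences. At 1,500 per arm the loss is already 6 to 8 points at OR 1.3 and nil at 1.5. Two of the three pairwise contrasts set people given an app against people not given one, where a shift as small as 1.2 need not be expected. This stands.

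Nor would direction be lost. The planned summary measures and graphs would show which way use moved, even though the test itself does not.

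The items are also blunt. Their recall window is 6 months, so at the 6-week survey about 20 of 26 recalled weeks precede enrolment, and at 18 weeks about 8. They ask about any app of each kind, not the assigned one. Objective usage time is collected separately and is continuous. All of this lowers the stakes. None of it supplies a method for the ordered answers.

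**Conclusion.** The point holds as a minor, conditional gap in specification and efficiency. The plan names no method for ordered outcomes. If its chi-square is the ordinary unordered test, it discards the order of the app-use answers and has less power than the same data allow against a modest consistent shift: about 59% against 79% at OR 1.20 with 1,500 per arm. The loss matters for ORs of about 1.1 to 1.3 at up to 1,500 per arm, and with smaller arms it reaches further up that range (58–62% against 79–82% at OR 1.3 with 750). It is nil at OR 1.5 with 1,500 per arm.

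Every power figure rests on assumed alpha, allocation, category shares and effect size. A reader might take this as an error of validity; the documents and the check do not support that, since type I error is unaffected. The items are additional outcomes in a plan whose stated primary goal is feasibility, acceptability and estimation.

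**What to change.** Add one sentence to the Analysis Plan:

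*Ordered categorical outcomes, including the app-use frequency items, will be compared between arms with a proportional-odds model, reporting an odds ratio with 95% CI for each pairwise arm contrast (or with a Wilcoxon/Kruskal-Wallis test if proportional odds is clearly violated), with the full category distribution by arm shown; chi-square is kept for unordered categories.*

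The model and the rank tests should not be described as equivalent. The rank test corresponds to the score test of the model, which is why the power figures carry over, but it yields no odds ratio. With three arms a single odds ratio is not enough, hence one for each pair.

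The cost is that sentence; no new data are needed. The small downside is lower power against non-monotone differences, which the displayed distributions would reveal.
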